4.2.2 Secondary Endpoints

- The frequency of achieving a complete plus partial response or disease stabilization with the 2 drug combination by dose cohort. (Response will be assessed by cross sectional imaging after every 2 cycles and will be categorized according to RECIST 1.1 criteria)

4.2.3 Correlative Endpoints

- Immunoscore of mTOR pathway protein expression (S6, pS6, 4E-BP1, p-4E-BP1, eI4F, Akt, pAkt, raptor, rictor, PRAS40, mSin1, FKBP38, and IRS-1 and HIF1- α) in archival biopsy sample for all patients and in paired fresh tumor biopsy specimens in up to 15 patients treated at P2RD if a separate informed consent is obtained.
- Immunoscore of myb protein expression in archival tissue samples in patients with adenoidcystic cancer.
- Serum level of inflammatory and immunologic markers (IL-6, IL-8, IL-12, IFN- γ , TNF- α , sIL-2R- α , CD4+ and CD8+ T-cell, NK cell and Treg cells); markers of angiogenesis (circulating VEGF and soluble VEGFR) and level of the potent platelet aggregator, cathepsin G, will be performed in serial blood samples collected at baseline, at the end of cycle 1 and at the time of disease progression or first diagnosis of venous thromboembolism (in the case of cathepsin G) and correlated with lenalidomide therapy by dose cohort.

5 Investigational Plan

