Everolimus is a derivative of rapamycin, which acts as a signal transduction inhibitor. Its target is mammalian target of rapamycin (mTOR), a key serine-threonine kinase regulating protein synthesis and ultimately cell growth, cell proliferation, angiogenesis and survival.⁶ Downstream of PI3/AKT, mTOR is a component of the PI3K/AKT/mTOR pathway known to be dysregulated in numerous human malignancies. Molecular epidemiological studies demonstrate that, in addition to a high frequency in specific cancers, activation of the PI3K/AKT/mTOR pathway is frequently a characteristic of worsening prognoses (through increased aggressiveness), resistance to treatment, extension of disease and progression. Preclinical studies have confirmed the role of this pathway in tumor development. Gain of function models demonstrate that constitutive activation of kinases such as AKT can lead to the inexorable development of malignancies resembling those seen in patients characterized by frequent activation of the same kinase. This complemented the demonstration of the antitumor activity of kinase inhibitors acting *in vitro* and *in vivo*.

Experiments carried out in Novartis laboratories, as well as elsewhere, show that everolimus is capable of inhibiting the proliferation and growth of a wide spectrum of tumor cell lines and tumors, respectively. The antiproliferative effects of everolimus are achieved at nanomolar concentrations; which is easily achieved in patients treated at the doses used in clinical trials. An

important aspect of the antitumor effect of everolimus is its potential to act on tumor cells by directly inhibiting growth and indirectly by inhibiting angiogenesis.⁶ The observation of *in vivo* sensitivity of xenografts raised from cells demonstrating resistance to everolimus *in vitro* is attributable to the drug's potential to act on the vascular component of the supporting peritumoral stroma.⁶ The antiangiogenic property of everolimus was confirmed through experiments demonstrating the effect of everolimus in countering VEGF-induced proliferation of human umbilical endothelial cells (HUVEC) *in vitro*,⁷ VEGF-driven angiogenesis in a chamber implant murine model and revascularization in a murine orthotopic melanoma model.

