10.2 Datasets to be analyzed

Demographics

Subject demographics including age, sex, race, ethnicity, height, weight, disease information, and medical conditions will be summarized by cohort using descriptive statistics.

Extent of Drug Exposure

The total number of doses of lenalidomide and everolimus (mg), and total number of treatment cycles delivered will be summarized by dose level using descriptive statistics.

Efficacy Endpoints

The secondary endpoint of the trial is response rate. The best overall response rate as defined by the proportion of subjects who have had a CR or PR will be summarized by dose level. Any subject treated in the expansion phase with overall response assessment of partial or complete response will have the response confirmed by repeat assessment no less than 4 weeks after the criteria for response are first met. The RR will be summarized by dose level using descriptive statistics along with a 95% confidence interval.

Pharmacokinetic Parameters

Serum concentration of study drug will be determined by a validated method according to assessment schedules. The pharmacokinetic parameters will be summarized using descriptive statistics.

The concentrations of everolimus, lenalidomide and their clinically significant metabolic product will be summarized by dose level using descriptive statistic. The mean concentration for each dose level will be plotted on scheduled sample time. The following pharmacokinetic parameters will be estimated and reported for each agent according to dose level.

$AUC_{0 \rightarrow t}$ Area under the concentration-time curve from the time of dosing to the time of the last observation; $AUC_{0 \rightarrow \infty}$ Area under the concentration-time curve from the time of dosing extrapolated to infinity; C_{max} Maximum serum concentration observed postdose; T_{max} Time point at which the C_{max} occurs; $t_{1/2}$ Elimination half-life, determined as $0.693/\lambda_z$.

Pharmacodynamic Correlates

The levels of mTOR pathway proteins, inflammatory cytokines and lymphocyte subsets at each specified time point will be reported in a descriptive manner for each dose schedule and analyzed by tumor type, when appropriate. Data will also be explored graphically. The PK and

pharmacodynamic data will be used to describe potential relationships between plasma levels of everolimus and or lenalidomide and changes in serum protein, toxicities, and tumor response.

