10.3 Statistical Methodology

All data will be listed individually by subject. Continuous variables will be summarized using descriptive statistics: mean, standard deviation, median, and minimum and maximum values. Categorical variables will be summarized using number of subjects and proportion expressed as percentage. Baseline value for any specified variable is the last valid measurement before the administration of the study drug. Unless otherwise indicated, statistical significance will be declared if the two-sided p value is ≤ 0.05 .

The estimation of pharmacokinetic parameters will be performed using WinNonlin® Version 5.0 or higher. All statistical analyses will be performed using SAS® Version 9.13 or higher.

Changes in immunological markers between baseline and C2D1 samples will be compared for each patient and for each dose cohort. In addition, mTOR pathway protein expression in baseline diagnostic biopsy samples will be assessed by Immunohistochemistry (IHC) and correlated with response. The dynamic changes in biomarker expression before and after one cycle of treatment with the drug combination will be summarized using summary statistics mean and standard deviation. Comparisons between the two time points will be presented graphically and subjected to statistical analysis using the Pearson's correlation coefficient.

Missing Data Handling

Unresolved missing data may be imputed when the analysis integrity is affected. The conservative principle will be used for data imputation. For example, if an adverse event onset day is missing but the adverse event onset year and month can not exclude this adverse event as a TEAE, the adverse event will be flagged as a TEAE.

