10.6 Sample size and power considerations

The sample size of up to 30 patients is required to establish the MTD and the RP2D based on the proposed modified Fibonacci dose escalation schema assuming that each dose cohort requires the maximum of 6 subjects. Up to 6 subjects will be enrolled at each dose level. If no DLTs occur, a total of 15 subjects will be needed to complete the dose escalation part of the study. To further characterize safety and efficacy, fifteen additional subjects will be enrolled at the MTD in an expansion cohort. In order to perform preliminary evaluation of anti-tumor activity, the sample size at the MTD or highest dose level cohort is determined by a power analysis. It is assumed that the subjects would have no response if they would not have received any therapy and that response rate for subjects in the MTD or highest dose level cohort would be 10%. Based on this assumption, a sample size of 15 subjects in the MTD cohort will provide more than 79% power in a one-sample exact binomial test at the significance level of 0.05. We anticipate accrual of 2-3 patients per month for the escalation phase and approximately 1-2 patients per month for the expansion phase, which is restricted to patients with clear cell renal cell carcinoma. At this accrual rate, we expect total accrual and study completion within 18-24 months.

A parallel expansion cohort of 9 patients with adenoidcystic carcinoma will also be evaluated. An objective response in at least 3 of 9 patients will be considered sufficient evidence to explore the benefit of this regimen in a larger phase II efficacy trial. The expected maximum overall sample size of 45 patients will still be maintained with the addition of this parallel cohort because only 21 of the maximum expected 30 patients were required in the dose escalation of the study.

11 Regulatory Considerations

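### Section 10.3 correlates 14 mTOR-pathway proteins with response at a default unadjusted 0.05, with no stated stratification and no multiplicity control (minor)

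*Combined protocol and SAP*

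**What the plan says.** - **Markers and patients.** Section 4.2.3 lists "Immunoscore of mTOR pathway protein expression (S6, pS6, 4E-BP1, p-4E-BP1, eI4F, Akt, pAkt, raptor, rictor, PRAS40, mSin1, FKBP38" and, in the same sentence, IRS-1 and HIF1-α, which makes 14 proteins. They are scored "in archival biopsy sample for all patients". Section 10.6 caps the trial at 45 patients.
- **Analysis.** Section 10.3 says "mTOR pathway protein expression in baseline diagnostic biopsy samples will be assessed by Immunohistochemistry (IHC) and correlated with response". It names no test, response coding, covariate or stratum for this. Pearson's coefficient is named only for the comparison of two time points.
- **Significance rule.** Sections 10.1 and 10.3 carry the same default: "Unless otherwise indicated, statistical significance will be declared if the two-sided p value is" ≤ 0.05. Nothing different is indicated for the proteins, and the analysis is not labelled exploratory.
- **Tumour type and dose.** Section 10.2 says the levels of these proteins, with cytokines and lymphocyte subsets, "will be reported in a descriptive manner for each dose schedule and analyzed by tumor type, when appropriate". It does not mention the relation to response at that point.
- **Aim.** The synopsis speaks of the ability of expression to predict the activity of everolimus. Section 4.1.3 asks only for a correlation.

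**The concern.** There are two separate problems.

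The first is multiplicity. Fourteen chances at 0.05, with no key protein and no adjustment, give an overall error rate far above 5%. A plan that words its aim as prediction invites the reader to take one small p value as an answer.

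The second is histology. Escalation admits any solid tumour at several dose levels. The expansion cohorts take renal, adenoid cystic and neuroendocrine tumours at the MTD or recommended phase II dose (section 5.1 and Table 1). Tumour type and dose therefore move together, and both may bear on response. Section 3.3 says that "in addition to a high frequency in specific cancers, activation of the PI3K/AKT/mTOR pathway is frequently a characteristic of worsening prognoses", so expression may also differ by tumour type. A correlation across all patients could then show a protein as related to response when it only marks tumour type.

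What is at stake is how the correlative results are read. Dose finding is not affected.

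**Working it through.** **Plan's own figures.** The documents give no error rate for the protein analyses. The sample size reproduces: 21 + 15 + 9 = 45, in line with "The expected maximum overall sample size of 45 patients will still be maintained with the addition of this parallel cohort". The one stated power, above 79% in section 10.6, also reproduces as 1 − 0.9^15 = 0.794, but it concerns response in the 15-patient cohort.

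**Step 1: independent tests, no true effect.**
- P(at least one p ≤ 0.05) = 1 − 0.95^14 = 0.512. With 13 tests it would be 0.487.
- Expected false positives = 14 × 0.05 = 0.7, whatever the correlation.

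**Step 2: correlated tests.** The documents give no inter-protein correlation, so it is varied (14 equicorrelated two-sided z tests, simulated).

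| Correlation | P(at least one) |
|---|---|
| 0.1 | 0.50 |
| 0.2 | 0.48 |
| 0.3 | 0.44 |
| 0.5 | 0.35 |
| 0.7 | 0.25 |
| 0.9 | 0.14 |

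**Step 3: small samples.** With 45 patients and an assumed 3 to 20 responders, a t test (equivalent to Pearson with a binary response) gives 0.51–0.53, 0.43–0.46 and 0.34–0.37 at correlation 0, 0.3 and 0.5. Fisher's exact test on a median split is mostly lower. Over correlations 0 to 0.5 it gives 0.00 with 3 responders, 0.42–0.50 with 5, 0.21–0.27 with 9 and 0.33–0.40 with 20.

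**Step 4: histology.** All inputs here are assumptions:
- 45 patients, with 24 of the expansion tumour types from the expansion cohorts.
- Response 5% in other tumours and 25% or 33% in expansion types.
- All 14 protein means shifted by 0.5 or 1 SD between the two groups, inter-protein correlation 0.3.
- No effect of any protein within a group.

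Sections 3.4 and 5.1 show that salivary gland tumours, adenoid cystic cancer among them, were enrolled in escalation. The number of the 21 escalation patients counted with the expansion types is therefore set at 0, 5 or 10. The entries are the per-protein error of an unstratified rank test (3,000 runs per setting).

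| Escalation patients of expansion types | 0.5 SD gap | 1 SD gap |
|---|---|---|
| 0 | 7–8% | 12–17% |
| 5 | 6–8% | 10–14% |
| 10 | 5.5–6.4% | 7–10% |

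Once some escalation patients are placed in their own tumour group, the range is roughly 5–14%. A rank test stratified by the two groups (van Elteren) returns about 5% per protein in every setting. The chance of at least one false protein then stays near 44%, so stratification alone does not deal with multiplicity.

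**Step 5: adjustment.** Bonferroni would use 0.05/14 = 0.0036 per test, for an overall error of 1 − (1 − 0.05/14)^14 = 4.9% under independence. Benjamini-Hochberg on the stratified tests gave about a 3% chance of any false claim in the clean 21 v 24 setting.

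**The case against.** The strongest reply is that this is correlative work in a phase I trial. Section 10.2 describes it as descriptive and graphical, section 10.3 names no test of protein against response, and the 0.05 rule is a general default. That stands as a reason to call the issue minor. It does not remove it, because the default applies unless something else is indicated, and nothing else is.

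Four stronger readings are tempting, and the documents do not support them:

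- A reader might infer that a false protein is more likely than not. That needs near-independence. The list holds total and phosphorylated forms of the same protein (S6, 4E-BP1, Akt) within one pathway, so positive correlation is likely, and the rate falls below one half once the correlation exceeds about 0.1.
- A reader might infer that the plan pools over tumour types and doses. It does not say so. Section 10.3 is silent, and section 10.2 allows analysis by tumour type where appropriate. The fair complaint is that stratification is not stated. Leaving it to later choice could add tests.
- A reader might add the 13 blood markers of section 4.2.3 to the same family. Those are tied to dose cohort and change over time, not to prediction of response.
- A reader might infer that a positive result is probably false, or would select the wrong patients later. An error rate under no effect is not the probability that a given finding is false, and no marker selects anyone. The phase II dose follows from the MTD, and the adenoid cystic rule in section 10.6 is 3 responses in 9 patients.

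A further objection concerns cost, and it is sound. Four tumour types by two dose groups makes up to eight strata in 45 patients. Under assumed inputs, eight strata with Benjamini-Hochberg as a gate leave only about 12–22% power for a 1 SD effect.

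**Conclusion.** The concern holds as a minor one. Following section 10.3 as written, with no true effect, gives about a 35–51% chance of at least one significant protein for tests of exact size at inter-protein correlations from 0.5 down to 0. At 0.3 to 0.5 that is about seven to nine times the nominal 5%. Higher correlation, or a coarse discrete test, would lower it.

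The histology effect is plausible from the design and from section 3.3. Its size, roughly 5–14% per protein, rests wholly on assumed response rates, marker gaps and tumour mix, and should be read as illustration. The MTD, the safety analysis and the phase II decision are untouched.

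**What to change.** In section 10.3:

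1. Make the main protein-response analysis a rank test stratified by a coarse tumour grouping, for example the expansion tumour types against all others. Assign escalation patients by their tumour and not by their phase. Give the pooled result descriptively, and say how dose level is shown.
2. Report Benjamini-Hochberg-adjusted p values across the 14 proteins beside the raw ones. State that no protein will be called predictive on an unadjusted p ≤ 0.05 alone, and that unadjusted results are hypothesis-generating.
3. Treat the 13 blood markers as a separate question about dose cohort and change over time.

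The cost is a few sentences and a little code, since tumour type and dose level are already recorded. Section 5.1.3 holds tissue for one batch at the end of the trial, so the wording can be settled before any protein result exists. Under assumed inputs, coarse stratification lowers power for a 1 SD effect only slightly (59% to 55%, or 72% to 67%). The loss is larger for any claim that must survive adjustment, which is why adjusted values are shown beside raw ones and do not decide what is reported.

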5.1 Overall design

This is a phase I, open-label, single institution, non-randomized study of escalating doses of daily, orally administered lenalidomide in combination with standard doses of everolimus, an orally available mTOR inhibitor. The trial is open to patients with advanced solid malignancies who have failed or are intolerant of available standard treatment options for their disease. Dose escalation will proceed in a modified Fibonacci 3+3 fashion with the requirement that dose escalation to the next level can only proceed if 0 of 3 or ≤ 1 of 6 patients experience a dose limiting toxicity (DLT). Four escalating dose cohorts and three deescalating dose cohorts will be used to evaluate different doses of lenalidomide and everolimus starting with the approved and or clinically relevant doses of both agents. The proposed starting dose level 1 is 10mg of lenalidomide (days 1 – 28) in combination with 10mg of everolimus (days 1 - 28) in a 28-day cycle. A serial de-escalation to 10mg of lenalidomide (days 1-21 of a 28 day cycle) and 5mg of everolimus will be carried out if DLT is observed in $\geq 33\%$ of patients enrolled to the starting dose cohort. The MTD is the highest dose level of lenalidomide and everolimus (up to a maximum dose of 25mg and 10mg respectively) at which $<33\%$ of the dose cohort experiences DLT after 1 cycle (28 days) of therapy. The established MTD will be the recommended dose for follow-up phase II study. To obtain preliminary clinical benefit of this combination, an expanded cohort of 15 patients with clear cell renal cell carcinoma, adenoidcystic carcinoma and neuroendocrine tumors will be treated at the define MTD. To allow for assessment of drug-drug interaction using PK analysis, lenalidomide will be administered alone on day 1 of the first cycle followed by both agents on day 2 cycle 1. Both drugs will be started simultaneously on day 1 of all subsequent cycles.

In addition, a parallel cohort of 9 additional patients with adenoicystic cancer will be treated at the RP2D. This is to enable us to obtain further evidence in support of the efficacy of this regimen in patients with adenoicystic cancer as observed in the limited number of patients with this cancer type who were enrolled in the escalation phase of the study.

Table 1

Dose Level	Lenalidomide (day 1 to 28)	Everolimus (day 1-28)	Patient Enrolment	Remarks
-2	10mg Days 1-21	5mg every other day	3 + 3	If DLT, study will close without defining a MTD
-1	10mg Days 1-21	5mg	3 + 3	Deescalate to level -2 if ≥ 1 of 6 patients experience DLT, otherwise declare as MTD and expand the cohort
Starting Dose 1	10mg	5mg	3 + 3	Escalate to level 2 if 0 of 3 or 1 of 6 patients experience DLT, otherwise deescalate 1 level
2	15mg	5mg	3 + 3	Escalate to level 3 if 0 of 3 or 1 of 6 patients experience DLT, otherwise deescalate 1 level
3	20mg	5mg	3 + 3	Escalate to level 4 if 0 of 3 or 1 of 6 patients experience DLT, otherwise deescalate 1 level
4	25mg	5mg	3 + 3	if ≥ 1 of 6 patients experience deescalate 1 level, otherwise declare as MTD
5	25mg	10	3 + 3	if ≥ 1 of 6 patients experience deescalate 1 level, otherwise declare as MTD
MTD	TBD	TBD	15	Expanded cohort of 15 patients restricted to patients with renal cell carcinoma, adenoicystic carcinoma and neuroendocrine tumors

5.1.1 Blood Sample Collection:

Blood samples will be collected in heparinized green top tubes (3 mls for PK samples and 7 mls for PBMC collection), red top tube (7 mls to obtain serum sample for cytokine assay). PBMC will be purified using standard Ficoll-Paque gradient centrifugation according to the instructions of the manufacturer (Amersham Pharmacia, Uppsala, Sweden). All samples must be stored away within 1 hour of collection by refrigeration at -80°C until ready for assay.

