This is a phase I, open-label, single institution, non-randomized study of escalating doses of daily, orally administered lenalidomide in combination with standard doses of everolimus, an orally available mTOR inhibitor. The trial is open to patients with advanced solid malignancies who have failed or are intolerant of available standard treatment options for their disease. Dose escalation will proceed in a modified Fibonacci 3+3 fashion with the requirement that dose escalation to the next level can only proceed if 0 of 3 or ≤ 1 of 6 patients experience a dose limiting toxicity (DLT). Five escalating dose cohorts and three deescalating dose cohorts (if DLT is encountered with the starting dose) will be used to evaluate different doses of lenalidomide and everolimus starting with the approved and or clinically relevant doses of both agents. The proposed starting dose level 1 is 10mg of lenalidomide in combination with 5mg of everolimus both administered on a once daily continuous dosing schedule for 28 days respectively in a 28-day cycle. A serial de-escalation to 10mg of lenalidomide (21 of 28 days) and 5mg of everolimus every other day will be carried out if DLT is observed in $\geq 33\%$ of patients enrolled to the starting dose cohort. The MTD is the highest dose level of lenalidomide and everolimus (up to a maximum dose of 25mg and 10mg respectively) at which $<33\%$ of the dose cohort experiences DLT after 1 cycle (28 days) of therapy. The established MTD will be the recommended dose for follow-up phase II study. To obtain preliminary evidence of potential clinical benefit of this combination, an expanded cohort of 15 patients with clear cell renal cell carcinoma, adenoidcystic carcinoma and neuroendocrine tumors will be treated at the defined MTD.

A parallel expansion cohort of 9 patients with adenoidcystic cancer will be treated at the RP2D

STUDY ENDPOINTS**Primary:**

- The MTD is the maximum doses of both drugs that can be administered without inducing DLT in $\geq 33\%$ of the treated patient cohort.
- Safety will be assessed according to NCI CTCAE 4.0v
- Assessment of DLT will be performed during the first cycle only and the following will constitute DLT in this study:
 - Grade 4 hematological toxicity lasting more than 7 days
 - Grade 4 Neutropenia of any duration in the presence of fever ≥ 38.5 c
 - Grade ≥ 3 nausea and or vomiting in spite of standard supportive therapy
 - Grade ≥ 3 non-hematologic toxicity (excluding alopecia)

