5.6.2 Dosing regimen

The planned starting dose of lenalidomide for investigation is 10 mg/day, orally on days 1 - 28 (28 day cycle). Dosing will be in the morning at approximately the same time each day. Prescriptions must be filled within 7 days. Subjects deemed by the Principal Investigator to be at heightened risk of venous thromboembolism will receive prophylaxis with daily aspirin (81mg or 325 mg) or low molecular weight heparin if intolerant to ASA. Coumadin should be used with caution and close monitoring of INR required.

If a dose of lenalidomide is missed, it should be taken as soon as possible on the same day. If it is missed for the entire day, it should not be made up. Patients who take more than the prescribed dose of lenalidomide should be instructed to seek emergency medical care if needed and contact study staff immediately.

The planned starting dose of everolimus (RAD001) is an approved dose of 5 mg/day on a continuous basis, days 1- 28. RAD001 will be self-administered (by the patients themselves). The investigator will instruct the patient to take the study drug exactly as specified in the protocol. RAD001 will be administered orally as once daily dose of 5 mg or 10 mg (one or two 5 mg tablets) starting from study day 2, cycle 1 until progression of disease or unacceptable toxicity. Patients will be instructed to take RAD001 in the morning, at the same time each day.

RAD001 may be taken with or without food.

If vomiting occurs, no attempt should be made to replace the vomited dose.

All dosages prescribed and dispensed to the patient and all dose changes during the study must be recorded.

Medication labels will comply with US legal requirements and be printed in English. They will supply no information about the patient. The storage conditions for study drug will be described on the medication label.

RAD001 will be provided by Novartis. RAD001 is formulated as tablets for oral administration of 5mg strength. Tablets are blister-packed under aluminum foil in units of 10 tablets, which should be opened only at the time of administration as drug is both hygroscopic and light-sensitive.

Subjects experiencing adverse events may need study treatment modifications (See section 5.7).

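### The Section 5.1 prose gives four escalation levels starting at everolimus 10 mg, while Table 1 and the synopsis give five starting at 5 mg, so the scheme behind the MTD needs reconciling

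*Combined protocol and SAP*

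**What the plan says.** The escalation scheme is described in six places in the combined protocol and SAP.

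- **Section 5.1, prose.** "Four escalating dose cohorts and three deescalating dose cohorts will be used to evaluate different doses of lenalidomide and everolimus". On the start: "The proposed starting dose level 1 is 10mg of lenalidomide (days 1 – 28) in combination with 10mg of everolimus".
- **Section 5.1, Table 1.** Levels 1 to 5 go upward and levels -1 and -2 downward. Level 1 is lenalidomide 10 mg with everolimus 5 mg. Everolimus stays at 5 mg through level 4 and is 10 mg only at level 5, with lenalidomide 25 mg. No row combines 10 mg of each drug. The rows for levels 1 to 3 say when to move up. The level 4 row says only when to step down and otherwise to declare the MTD.
- **Synopsis, Study Design.** "Five escalating dose cohorts and three deescalating dose cohorts (if DLT is encountered with the starting dose) will be used", and "The proposed starting dose level 1 is 10mg of lenalidomide in combination with 5mg of everolimus".
- **Section 5.6.2.** "The planned starting dose of everolimus (RAD001) is an approved dose of 5 mg/day on a continuous basis". It gives no number of levels.
- **Section 5.7.1, Table 4.** The row labelled as the everolimus starting dose is paired with 10 mg daily.
- **Section 10.6.** Escalation needs up to 30 patients at 6 per level, or 15 if no dose-limiting toxicity (DLT) occurs. The 9-patient adenoid cystic cohort fits within 45 "because only 21 of the maximum expected 30 patients were required in the dose escalation of the study". It gives no starting dose.

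**The concern.** The MTD is the primary endpoint, and Section 5.1 defines it as a dose level. Sections 10.2 and 10.4 summarise exposure, response and adverse events by dose level. These summaries need one agreed list of levels with one pair of doses for each. The current text has two definitions of level 1, which differ two-fold in everolimus, and two counts of the levels above it. Both sit in complete, legible operative text, one directly above the other in Section 5.1, so neither the amendment history nor the PDF conversion explains the difference.

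Two uses of the scheme are still live. One is the reporting of the MTD and the by-level results, including the dose given to the two expansion cohorts. The other is Table 4, which guides everolimus reductions for individual patients and takes a starting dose as its reference point.

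**Working it through.** **Step 1. The passages side by side.**

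| Place | Escalation levels | De-escalation levels | Everolimus at start |
|---|---|---|---|
| 5.1 prose | 4 | 3 | 10 mg |
| 5.1 Table 1 | 5 rows (no step from 4 to 5) | 2 | 5 mg |
| Synopsis | 5 | 3 | 5 mg |
| 5.6.2 | not given | not given | 5 mg |
| 5.7.1 Table 4 | not given | not given | 10 mg |
| 10.6 | 5, by arithmetic (step 2) | not given | not given |

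Only the synopsis and Table 1 carry both elements of the five-level, 5 mg version. Section 5.6.2 supports the dose alone and Section 10.6 the count alone. The 10 mg start appears in the 5.1 prose and in Table 4.

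**Step 2. Reproduce the Section 10.6 figures.** Inputs: at most 6 patients per level and an expansion cohort of 15 (both Section 10.6), and 3 per level when no DLT occurs (the 3+3 rule in Section 5.1).

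- Maximum = levels × 6. Five levels: 5 × 6 = 30, as stated.
- Minimum = levels × 3. Five levels: 5 × 3 = 15, as stated.
- Maximum plus expansion: 30 + 15 = 45, as stated.

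**Step 3. The same formulas with the count in the 5.1 prose.**

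- Maximum: 4 × 6 = 24, not 30.
- Minimum: 4 × 3 = 12, not 15.

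If the level 4 row of Table 1 is followed literally, escalation also ends after four levels and gives the same 24 and 12.

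**Step 4. The 9-patient cohort.** Section 10.6 takes it from unused escalation places: 30 − 21 = 9. With four levels the unused places would be 24 − 21 = 3. The four-level text therefore does not support the maximum on which the justification rests. The total itself is a plain sum, 21 + 15 + 9 = 45, and does not depend on the number of levels.

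**Step 5. Does the figure of 21 show which scheme was run?** No. Assuming full cohorts of 3 or 6, no replaced patients and no de-escalation, 6 + 6 + 6 + 3 = 21 is possible with four levels and 6 + 6 + 3 + 3 + 3 = 21 with five. Only the dosing records can settle it.

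**The case against.** The strongest reply has four parts.

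**The total is not in dispute.** A reader might infer from 24 + 15 = 39 that the trial has a second cap of 39 and that 45 exceeds it by 6. The documents do not support that. The synopsis, Section 5.4 and Section 10.6 all give 45. The figure 39 appears only in the list of changes, as a superseded number. This part stands in full.

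**Table 1 is already the named schema.** Section 5.6.1 assigns patients by Table 1, and Sections 5.7.1 and 5.7.3 refer cohort decisions to it. The prose defines doses only for level 1; levels 2 to 5, -1 and -2 have their doses in Table 1. It would therefore be too strong to say that a level number identifies no dose. This stands in large part, but it does not close the matter: Table 1 has its own gap at level 4, has one de-escalation level fewer than the text promises, and disagrees with Table 4 on the everolimus start.

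**Escalation is finished.** Section 10.6 speaks of it in the past tense, and Section 3.4 reports patients already enrolled in that phase. A reader might infer that future patients could start at twice the intended everolimus dose. The documents do not support this, because remaining accrual is at the MTD or recommended phase II dose. This stands.

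**The de-escalation targets need not conflict.** Section 5.1 names everolimus 5 mg and the synopsis 5 mg every other day. Both describe a serial step-down, and these doses match levels -1 and -2 of Table 1, so they can be two steps of one sequence. This stands. The count of three against two does not go away.

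**Conclusion.** The point holds as an inconsistency in the description of the escalation scheme, and it should be corrected. The everolimus dose at level 1 differs two-fold (10 mg against 5 mg). The escalation levels number four or five, and the de-escalation levels three or two. Section 10.6 reproduces exactly with five levels (30, 15 and 45) and not with four (24 and 12). The conflict is not a single stray word in Section 5.1, because Table 4 and the level 4 row of Table 1 share in it.

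The sample size is not wrong, and no analysis needs more patients. With escalation complete, the remaining effect is on identifying and reporting the MTD and by-level results, and on the reference point for individual dose reductions.

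This rests on reading Tables 1 and 4 as they appear in the document, and on 3 or 6 patients per level with no replacements counted. It takes no position on which starting dose, number of levels or step rule is right.

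**What to change.** In the next amendment, reconcile six places so that they describe one scheme: the Section 5.1 prose, the synopsis, Table 1 (including the level 4 row and the number of de-escalation levels), Section 5.6.2, Table 4 and Section 10.6. Verify the reconciled scheme against the dosing records of the 21 escalation patients; the pill diary in Appendix Y has fields for the cohort number and the original dose of both drugs. Report the MTD and all by-level results with the actual mg doses of lenalidomide and everolimus beside any level number.

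The cost is about a paragraph of text with matching table edits, and a check of existing records. No new patients or data are needed. The sponsor must decide which passages reflect the scheme that was intended and followed.
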